## 6.5. Multiple Comparisons/Multiplicity

A multiple testing strategy for the primary and major secondary objectives will be implemented to control the family-wise type I error rate at a 2-sided  $\alpha$  level of 0.05. The primary outcomes of ASAS40 at Week 16 (for regulatory agencies that accept Week 16 as primary endpoint) and ASAS40 at Week 52 (for regulatory agencies that require Week 52 as primary endpoint) will be tested. These tests will use the primary analysis method, logistic regression analysis with treatment, geographic region, and screening MRI/CRP status in the model, with NRI missing data imputation approach. Because this study has different primary endpoints for different regulatory agencies, the significances of both primary endpoints will not be required in order for the study to be considered successful. No further multiplicity adjustment will be made for the 2 primary endpoints.

Since Study RHBX is conducted to meet registration requirements from various regulatory agencies, 2 separate lists of primary and major secondary outcomes are created and multiplicity adjustment is conducted within each of the lists [each list will be tested at a total alpha of 0.05], using the graphical multiple testing procedure (Bretz et al. 2011). This graphical approach is a closed testing procedure; hence, it strongly controls the family-wise error rate (Alosh et al. 2014).

### 6.5.1. For regulatory agencies that accept Week 16 endpoints for approval purposes

For regulatory agencies that accept Week 16 endpoints for approval purposes, the following is the list of primary and major secondary outcomes to be tested for both ixekizumab 80 mg Q2W and Q4W regimens at Week 16:

- Primary - proportion of patients achieving an ASAS40 response [ASAS40] at Week 16
- Secondary 1 - change from baseline in ASDAS score [ASDAS CFB] at Week 16
- Secondary 2 - change from baseline in BASDAI [BASDAI CFB] at Week 16
- Secondary 3 - change from baseline in SF-36 PCS [SF-36 PCS CFB] at Week 16
- Secondary 4 - proportion of patients achieving ASDAS low disease activity [ASDAS  $< 2.1$ ] at Week 16
- Secondary 5 - change from baseline in MRI of the SI joint SPARCC score [MRI SPARCC SIJ CFB] at Week 16

The 5 major secondary outcomes are grouped into 2 tiers for testing ([Figure RHBX.6.2](#)).

[figure not shown]
Figure RHBX.6.1 shows the graphical testing scheme with initial  $\alpha$  allocation and weights, and Figure RHBX.6.2 shows the graphical testing schemes used within the Tier 1 and Tier 2 groups of endpoints. All comparisons are at Week 16. The testing steps are outlined below:

The primary outcome of ASAS40 at Week 16 will be initially tested for ixekizumab 80 mg Q2W versus placebo at a 2-sided  $\alpha=0.02$ , and for ixekizumab 80 mg Q4W versus placebo at a 2-sided  $\alpha=0.03$ . If neither null hypothesis can be rejected, no further testing is conducted as the  $\alpha$  for the test of ixekizumab 80 mg Q2W versus placebo and the  $\alpha$  for the test of ixekizumab 80 mg Q4W versus placebo are considered ‘spent’ and cannot be passed to other endpoints.

If at least one of these null hypotheses can be rejected at the corresponding  $\alpha$  levels, the testing continues for the remaining outcomes according to the procedure specified by the graphs, by allocating the remaining  $\alpha$  to the next set of outcomes as long as at least one hypothesis can be rejected. Each time a hypothesis is rejected, the graph is updated to reflect the reallocation of  $\alpha$ , which is considered “recycled” (Alosh et al. 2014). This iterative process of updating the graph and reallocating  $\alpha$  is repeated until all major secondary hypotheses have been tested or when no remaining hypotheses can be rejected at their corresponding  $\alpha$  level. The weights along the edges for  $\alpha$  allocation between ixekizumab 80 mg Q2W and ixekizumab 80 mg Q4W outcomes as well as within each of the tiers are prespecified in Figure RHBX.6.1 and Figure RHBX.6.2.

[figure not shown]
Multiple testing scheme for regulatory agencies that accept Week 16 endpoints for approval purposes:

*All outcomes are assessed at Week 16:*

Abbreviations: ASAS = Assessment of Spondyloarthritis International Society; Q2W = every 2 weeks; Q4W = every 4 weeks; wk = week.

**Figure RHBX.6.1. Graphical multiple testing scheme for regulatory agencies that accept Week 16 endpoints for approval purposes.**

Abbreviations: ASDAS = Ankylosing Spondylitis Disease Activity Score; BASDAI = Bath Ankylosing Spondylitis Disease Activity Index; CFB = change from baseline; MRI = magnetic resonance imaging; SIJ = sacroiliac joints; Q2W = every 2 weeks; Q4W = every 4 weeks; SPARCC = Spondyloarthritis Research Consortium of Canada; SF-36 PCS = Short Form 36 physical component score; Wk = Week.

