**Statistical Analysis:**

Approximately 300 patients will be randomized at a 1:1:1 ratio in the Blinded Treatment Dosing Period (Period 2) to ixekizumab 80 mg Q2W, ixekizumab 80 mg Q4W, and placebo. In the active treatment groups, half the patients will be given a 160-mg starting dose and the other half will be given an 80-mg starting dose. With 100 patients per treatment group, this study will have approximately 98% power to test the superiority of ixekizumab Q2W to placebo for ASAS40 at Week 16. The following assumptions were used for the power calculations for ASAS40 response rates at Week 16 regardless of ixekizumab starting dose: 46% for ixekizumab 80 mg Q2W treatment group and 18% for the placebo group. A 2-sided Fisher's exact test at the 0.05 level is assumed.

There is little data from similarly designed 52-week placebo-controlled trials regarding the ASAS40 response rate for active and placebo treated patients to guide power estimation at Week 52. With 100 patients per treatment group, this study will have approximately 66-99% power to test the superiority of ixekizumab Q2W to placebo for ASAS40 at Week 52, assuming various ASAS40 response rates for ixekizumab Q2W and placebo at Week 52. A 2 sided Fisher's exact test at the 0.05 level is assumed.

The efficacy analyses for the Blinded Treatment Dosing Period will be conducted on the intent-to-treat (ITT) population and safety analyses will be conducted on the safety population.

Comparisons between each ixekizumab treatment group (80 mg Q2W or 80 mg Q4W) and placebo will be performed for all analyses in the Blinded Treatment Dosing Period. Unless otherwise specified, the ixekizumab 80 mg Q2W and 80 mg Q4W groups will be analyzed without regard to starting dose. The primary analysis method for treatment group comparisons of categorical efficacy and health outcomes variables will be a logistic regression analysis with treatment, geographic region, and screening MRI/CRP status (positive MRI and elevated CRP; positive MRI and nonelevated CRP; negative MRI and elevated CRP) as factors, using the Nonresponder Imputation (NRI) method.

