### **9.2.5. Adjustment for Multiple Comparisons**

The primary outcome of ASAS40 at Week 16 will be tested for ixekizumab 80 mg Q2W versus placebo at a 2-sided  $\alpha=0.05$ . The primary outcome of ASAS40 at Week 52 will also be tested for ixekizumab 80 mg Q2W versus placebo at a 2-sided  $\alpha=0.05$ . Because this study has a different primary endpoint for different regulatory agencies, the significances of both primary endpoints will not be required in order for the study to be considered successful. No multiplicity adjustment will be made for the 2 primary endpoints. The comparison of ASAS40 for ixekizumab 80 mg Q4W versus placebo at Weeks 16 and Week 52 and the major secondary objectives (Section 3) will be tested using an appropriate multiple testing approach providing strong control of the familywise error rate (for the primary and major secondary tests) at a 2-sided  $\alpha=0.05$ . Details of the specific testing methodology (including testing order, interrelationships, type I error allocation, and the associated propagation) will be specified in the SAP.

There will be no adjustment for multiple comparisons for any other analyses.

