Unless otherwise specified, treatment groups of ixekizumab 80 mg Q2W and Q4W will be analyzed without regard to starting dose.

The primary analysis method for treatment comparisons of categorical efficacy and health outcomes variables at specific time points will be made using a logistic regression analysis with treatment, geographic region (Europe and non-Europe), and screening MRI/CRP status in the model using PROC Logistic with a Wald test. The odds ratio and 95% CIs will be reported; treatment difference and 95% CI will also be reported. Secondary analysis will be conducted using a Fisher's exact test. In the case when logistic regression model does not produce statistical results due to sparse data, Fisher's exact test will be used.

As a secondary analysis for the primary and major secondary categorical efficacy measures, a categorical, pseudo-likelihood based mixed-effects model of repeated measures (categorical mixed-effects model of repeated measures [MMRM]) estimating the percentage of patients achieving response across postbaseline visits may be used. The model will include treatment, geographic region, screening MRI/CRP status, visit, and treatment-by-visit as fixed factors. The binomial distribution and the logit link will be used. The restricted maximum likelihood (REML) will be used. An unstructured covariance matrix will be used to model the within-patient variance-covariance errors. The Kenward-Roger approximation will be used to estimate the denominator degrees of freedom. The Newton-Raphson with ridging optimization technique will be used to aid with convergence. The probability of response, the corresponding 2-sided 95% CI, and the p-value for treatment comparisons at Week 16 (Visit 8), Week 52 (Visit 15), and all other postbaseline visits will be reported.

If the unstructured covariance matrix results in a lack of convergence, the heterogeneous Toeplitz covariance structure, followed by the heterogeneous autoregressive covariance structure, followed by the compound symmetry will be used. This order is specified according to a decreasing number of covariance parameters in the structure. The sandwich estimator (Diggle et al. 1994) for the covariance estimation will be used by specifying the EMPIRICAL option in SAS PROC MIXED. When sandwich estimation is used, the Kenward-Roger approximation for denominator degrees of freedom cannot be used. Instead, DDFM= BETWITHIN option will be used to estimate denominator degrees of freedom.

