**Figure RHBX.6.2. Graphical multiple testing scheme used within the Tier 1 and Tier 2 group of endpoints.**

### 6.5.2. For regulatory agencies that require Week 52 endpoints for approval purposes

For regulatory agencies that require Week 52 endpoints for approval purposes, the following is the list of primary and major secondary outcomes to be tested for both ixekizumab 80 mg Q2W and Q4W regimens at Week 52. Note that ASAS40 will also be tested at Week 16 as a major secondary endpoint in addition to be tested at Week 52 as a primary endpoint. In addition, MRI SPARCC of SIJ will be tested at W16:

- Primary - proportion of patients achieving an ASAS40 response [ASAS40] at Week 52
- Secondary 1 - proportion of patients achieving an ASAS40 response at Week 16
- Secondary 2 - change from baseline in ASDAS score [ASDAS CFB] at Week 52
- Secondary 3 - change from baseline in BASDAI [BASDAI CFB] at Week 52
- Secondary 4 - change from baseline in SF-36 PCS [SF-36 PCS CFB] at Week 52

- Secondary 5 - proportion of patients achieving ASDAS low disease activity [ASDAS <2.1] at Week 52
- Secondary 6 - change from baseline in MRI of the SI joint SPARCC score [SPARCC CFB] at Week 16

The 6 major secondary outcomes are grouped into 2 tiers for testing ([Figure RHBX.6.4](#)).

[Figure RHBX.6.3](#) shows the graphical testing scheme with initial  $\alpha$  allocation and weights, and [Figure RHBX.6.4](#) shows the graphical testing schemes used within the Tier 1 and Tier 2 groups of endpoints. All comparisons are at Week 52 unless otherwise noted on the graphs. The testing steps are outlined below:

Step 1: The primary outcome of ASAS40 at Week 52 will be tested for ixekizumab 80 mg Q2W versus placebo at a 2-sided  $\alpha=0.05$ . If the null hypothesis is not rejected, no further testing is conducted, as the  $\alpha$  for that test is considered “spent” and cannot be passed to other endpoints. If the null hypothesis is rejected, then move to Step 2.

Step 2: The primary outcome of ASAS40 at Week 52 will be tested for ixekizumab 80 mg Q4W versus placebo at a 2-sided  $\alpha=0.05$ . If the null hypothesis is not rejected, no further testing is conducted, as the  $\alpha$  for that test is considered “spent” and cannot be passed to other endpoints. If the null hypothesis is rejected, then move to Step 3.

[figure not shown]

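### For ixekizumab Q2W versus placebo on ASAS40 at Week 16, Protocol 9.2.5 sets a two-sided alpha of 0.05 but SAP 6.5.1 starts the test at 0.02, and the power statements still quote 0.05

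*SAP*

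**What the plan says.** **Protocol 9.2.5 (amendment b).** "The primary outcome of ASAS40 at Week 16 will be tested for ixekizumab 80 mg Q2W versus placebo at a 2-sided" alpha of 0.05. The section then sends the Q4W comparisons at Weeks 16 and 52 and the major secondary objectives to a multiple testing approach with strong familywise control at 0.05. It closes: "Details of the specific testing methodology (including testing order, interrelationships, type I error allocation, and the associated propagation) will be specified in the SAP".

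**SAP 6.5.1, the Week 16 list.** "The primary outcome of ASAS40 at Week 16 will be initially tested for ixekizumab 80 mg Q2W versus placebo at a 2-sided" alpha of 0.02, and Q4W at 0.03. If neither null is rejected, testing stops. If at least one is, it continues: "Each time a hypothesis is rejected, the graph is updated to reflect the reallocation of" alpha. The edge weights are in Figure RHBX.6.1, which is not visible in the text available for this review.

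**SAP 6.5.2, the Week 52 list.** "The primary outcome of ASAS40 at Week 52 will be tested for ixekizumab 80 mg Q2W versus placebo at a 2-sided" alpha of 0.05, as in the protocol. Q4W follows at 0.05, and all testing stops if Q4W is not rejected.

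**The deciding test.** SAP 6.5: "These tests will use the primary analysis method, logistic regression analysis with treatment, geographic region, and screening MRI/CRP status in the model", with nonresponder imputation. SAP 6.1.2.1 specifies "screening MRI/CRP status in the model using PROC Logistic with a Wald test".

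**Power.** The protocol synopsis states: "this study will have approximately 98% power to test the superiority of ixekizumab Q2W to placebo for ASAS40 at Week 16". Protocol 9.1 and SAP 5.2 give the same figure. All three assume 46% versus 18%, 100 patients per arm and a two-sided Fisher's exact test at 0.05.

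**Revision history.** The SAP entry for Section 6.5 attributes the new scheme to the protocol amendment and to changed major secondary objectives. It does not mention a Q2W threshold other than 0.05.

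**The concern.** The endpoint, comparison and visit are the same in both documents, but the significance level is not. This is a primary hypothesis for agencies that accept Week 16, so the level decides whether the trial is called a success for them. If Q2W gave p = 0.03 and Q4W missed 0.03, the sponsor would hold two prespecified documents with opposite answers, and any choice made after unblinding would look driven by the result.

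The SAP is also out of step with itself. Its only Week 16 power figure is quoted at 0.05, a level that its own Week 16 scheme does not initially give to Q2W.

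**Working it through.** **Inputs.** From Protocol 9.1 and SAP 5.2: n = 100 per arm, 46% for Q2W and 18% for placebo. From Protocol 9.2.5: alpha 0.05 for Q2W. From SAP 6.5.1: 0.02 for Q2W and 0.03 for Q4W. Neither document gives a Week 16 Q4W rate or a lower Q2W rate, so the Q4W rates and every 40% or 36% rate below are assumptions. Covariate distributions are not available, so the Wald test is computed without region and MRI/CRP status.

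**Step 1: reproduce the stated power.** Sum the binomial probabilities over all pairs of responder counts for which the test rejects, at 46% versus 18%.

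| Two-sided alpha | Fisher's exact test | Logistic Wald test |
|---|---|---|
| 0.05 | 98.8% | 99.2% |
| 0.03 | 97.9% | 98.5% |
| 0.02 | 96.9% | 97.8% |

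The stated figure of approximately 98% at 0.05 reproduces to within about one point. At the SAP's initial 0.02 it is 1.1 points lower by Fisher (98 − 96.9) and still rounds to 98% by Wald.

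**Step 2: which observed results fall between the two thresholds.** With a and c responders out of 100 on Q2W and placebo:

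z = [ln(a/(100−a)) − ln(c/(100−c))] / √(1/a + 1/(100−a) + 1/c + 1/(100−c))

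Take c = 18:
- a = 30: z = 0.669/0.340 = 1.97, p = 0.049
- a = 31: p = 0.034
- a = 32: z = 0.763/0.337 = 2.26, p = 0.024
- a = 33: p = 0.016

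So 30, 31 or 32 Q2W responders against 18 on placebo meet 0.05 and miss 0.02.

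**Step 3: when the verdicts must differ.** If Q4W is rejected at 0.03, alpha is reallocated, and whether Q2W then reaches 0.05 depends on weights that cannot be seen. If Q4W is not rejected at 0.03, nothing can be recycled to Q2W, and a Q2W p-value between 0.02 and 0.05 fails under the SAP whatever the weights are. The certain disagreement is therefore

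0.02 < p(Q2W) ≤ 0.05 and p(Q4W) > 0.03.

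**Step 4: how likely that is.** Joint enumeration with the Wald test and one shared placebo arm at 18%:

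| Q2W rate | Q4W rate (assumed) | Chance of opposite verdicts |
|---|---|---|
| 46% (planned) | 46% | 0.13% |
| 46% (planned) | 40% | 0.52% |
| 46% (planned) | 36% | 0.88% |
| 40% (assumed) | 40% | 1.46% |
| 36% (assumed) | 36% | 4.00% |

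**Step 5: error control.** 0.02 + 0.03 = 0.05, so the SAP's Week 16 list spends exactly its total.

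**Step 6: the alternative of Q2W at 0.05 and then Q4W at 0.05.** If Week 16 copied SAP 6.5.2, a Q4W miss would end all testing, including the Q2W secondaries. The chance that Q2W succeeds at 0.05 and Q4W misses 0.05, with Q2W at 46%, is 0.7%, 6.0% and 17.0% for assumed Q4W rates of 46%, 40% and 36%.

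**The case against.** The best defence is delegation. Protocol 9.2.5 hands type I error allocation and its propagation to the SAP, Protocol 9.2 says that the SAP holds the complete details, and the synopsis puts the primary objectives, which cover both regimens, under the multiple testing strategy. The SAP was revised after amendment (b), and its Week 16 rule is unambiguous. An analyst would follow it, and what is left is a protocol sentence that was not updated. Much of this stands, and it lowers the weight of the point. It does not remove it: Protocol 9.2.5 names Q4W and the major secondaries as what goes to the testing scheme and gives Q2W its own 0.05, and SAP 6.5.2 keeps that 0.05 at Week 52.

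A second objection is that the power figure survives. That is right. The Wald test decides the verdict, and its power at 0.02 is 97.8%; with full recycling and both regimens at 46% it would be 99.0%. Only the alpha quoted beside the 98% is out of date.

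A reader might also infer that the protocol forbids success on Q4W alone, which the SAP permits, and count those outcomes as conflicts too. The protocol states no testing order, so that reading is an inference and adds nothing to the size given here.

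**Conclusion.** The two documents give different significance levels for one primary test, and the Week 16 text is wrong as written. The firm consequence is confined to a Q2W p-value between 0.02 and 0.05 with a Q4W p-value above 0.03. At the planned Q2W rate of 46% the chance of this is 0.1% to 0.9%, for a Q4W rate assumed between 46% and 36%. It reaches 4.0% if both regimens are assumed to respond at 36%. These figures rest on 100 patients per arm, 18% on placebo and an unadjusted Wald test.

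Three stronger readings are not supported:
- Type I error is not inflated within the Week 16 list, because the split sums to 0.05.
- The sample size is not shown to be too small: power at 0.02 is 96.9% by Fisher and 97.8% by Wald.
- Not every Q2W p-value between 0.02 and 0.05 is a conflict. Where Q4W is rejected, the SAP outcome depends on the weights in Figure RHBX.6.1.

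The effect is small under the planning assumptions. It should still be fixed, because a primary threshold has to be the same in both documents before the data are seen.

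**What to change.** Before unblinding:

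1. Amend the Week 16 sentence in Protocol 9.2.5 to the SAP rule: Q2W initially at 0.02, Q4W at 0.03, with recycling as in Figure RHBX.6.1.
2. Declare the change of Q2W threshold in the SAP revision history.
3. In the synopsis, Protocol 9.1 and SAP 5.2, quote Week 16 Q2W power at the initial alpha of 0.02, naming the test: about 97% by Fisher's exact test, or about 98% by the logistic Wald test that decides the verdict.

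Protocol 9.2 requires an amendment only for a principal feature. The alpha of a primary endpoint can reasonably be called one. If the sponsor disagrees, the same section requires the change and its justification in the clinical study report.

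The cost is wording only: one protocol sentence, three power statements and one revision-history entry, with no patients and no new data.

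If the sponsor would rather keep 0.05 for Q2W and then test Q4W at 0.05 in SAP 6.5.1, the existing power statements can stay, but Q4W could no longer succeed alone. The SAP must then also say whether a Q4W miss stops testing of the Q2W secondaries. Copying SAP 6.5.2 would do so, in 0.7% to 17.0% of trials under the assumptions in the working, whereas the present Week 16 rule stops only if neither regimen is rejected.

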**Figure RHBX.6.2. Graphical multiple testing scheme used within the Tier 1 and Tier 2 group of endpoints.**

### 6.5.2. For regulatory agencies that require Week 52 endpoints for approval purposes

For regulatory agencies that require Week 52 endpoints for approval purposes, the following is the list of primary and major secondary outcomes to be tested for both ixekizumab 80 mg Q2W and Q4W regimens at Week 52. Note that ASAS40 will also be tested at Week 16 as a major secondary endpoint in addition to be tested at Week 52 as a primary endpoint. In addition, MRI SPARCC of SIJ will be tested at W16:

- Primary - proportion of patients achieving an ASAS40 response [ASAS40] at Week 52
- Secondary 1 - proportion of patients achieving an ASAS40 response at Week 16
- Secondary 2 - change from baseline in ASDAS score [ASDAS CFB] at Week 52
- Secondary 3 - change from baseline in BASDAI [BASDAI CFB] at Week 52
- Secondary 4 - change from baseline in SF-36 PCS [SF-36 PCS CFB] at Week 52

- Secondary 5 - proportion of patients achieving ASDAS low disease activity [ASDAS <2.1] at Week 52
- Secondary 6 - change from baseline in MRI of the SI joint SPARCC score [SPARCC CFB] at Week 16

The 6 major secondary outcomes are grouped into 2 tiers for testing ([Figure RHBX.6.4](#)).

[Figure RHBX.6.3](#) shows the graphical testing scheme with initial  $\alpha$  allocation and weights, and [Figure RHBX.6.4](#) shows the graphical testing schemes used within the Tier 1 and Tier 2 groups of endpoints. All comparisons are at Week 52 unless otherwise noted on the graphs. The testing steps are outlined below:

Step 1: The primary outcome of ASAS40 at Week 52 will be tested for ixekizumab 80 mg Q2W versus placebo at a 2-sided  $\alpha=0.05$ . If the null hypothesis is not rejected, no further testing is conducted, as the  $\alpha$  for that test is considered “spent” and cannot be passed to other endpoints. If the null hypothesis is rejected, then move to Step 2.

Step 2: The primary outcome of ASAS40 at Week 52 will be tested for ixekizumab 80 mg Q4W versus placebo at a 2-sided  $\alpha=0.05$ . If the null hypothesis is not rejected, no further testing is conducted, as the  $\alpha$  for that test is considered “spent” and cannot be passed to other endpoints. If the null hypothesis is rejected, then move to Step 3.

[figure not shown]
Step 3:  $\alpha=0.02$  ( $0.4*0.05$ ) will be distributed to Tier 1 set of secondary outcomes for ixekizumab 80 mg Q2W (blue circles in [Figure RHBX.6.4](#)), and the remaining  $\alpha=0.03$  ( $0.6*0.05$ ) will be distributed to Tier 1 set of secondary outcomes for ixekizumab 80 mg Q4W (orange circles in [Figure RHBX.6.4](#)).

The major secondary endpoints for both doses will be tested according to the procedure specified by the graphs.

The testing process continues for the remaining outcomes by allocating the remaining  $\alpha$  to the next set of outcomes as long as at least 1 hypothesis can be rejected. Each time a hypothesis is rejected, the graph is updated to reflect the reallocation of  $\alpha$ , which is considered “recycled” (Alosh et al. 2014). This iterative process of updating the graph and reallocating  $\alpha$  is repeated until all major secondary hypotheses have been tested or when no remaining hypotheses can be rejected at their corresponding  $\alpha$  level. The weights along the edges for  $\alpha$  allocation between ixekizumab 80 mg Q2W and ixekizumab 80 mg Q4W outcomes as well as within each of the tiers are prespecified in [Figure RHBX.6.3](#) and [Figure RHBX.6.4](#).

[figure not shown]
